### **6.3. Early Termination Visit and Follow-up Visit**

All patients withdrawing from the study prior to Week 104 will complete an Early Termination visit. The Early Termination visit procedures are identical to those of Week 104. An endometrial biopsy is required for all patients at the Early Termination visit except for patients whose last dose of study drug was taken during Week 32 or earlier or within four weeks after completion of the Week 52 endometrial biopsy. However, the endometrial biopsy may be obtained if it will aid in the evaluation of an ongoing adverse event.. Bone densitometry may be performed at the investigator's discretion, if it aids in follow-up of an ongoing adverse event(s). Follow-up bone densitometry findings for patients who terminate from the study early will proceed according to the rules provided in Section 6.5.2.6.

Patients (including those who complete the Week 104 visit and those who withdraw early from this study) will have a Follow-up visit approximately 30 days after the last dose of study drug, or prior to the date of initiation of another investigational agent or hormonal therapy affecting the hypothalamic-pituitary-gonadal axis or surgical intervention or other invasive procedure for endometriosis, whichever occurs first. However, for patients who enroll directly into another relugolix clinical study upon completion of the Week 104 visit, the Follow-up visit may be waived.

The Follow-up visit will be used to assess safety after discontinuation of study treatment including adverse events, clinical safety laboratories, and return of menstruation. Refer to the Schedule of Activities (see Section 1.1) for individual study visit procedures during the Follow-up visit.

Follow-up of bone densitometry findings for patients who terminate from the study early will proceed according to the rules provided in Section 6.5.2.6.

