- s Determination of bone mineral density by DXA at Early Termination and follow-up of findings will proceed based on the timing of the Early Termination visit. For Early Termination occurring after Week 24 and before Week 36, DXA is not required at Early Termination visit unless it will aid in the assessment of an adverse event, and follow-up DXA required at 6 months ( $\pm$  1 month) if most recent DXA bone mineral density loss at lumbar spine (L1-L4) or total hip was  $>$  2% relative to the parent study baseline. For Early Termination occurring after Week 36 and before Week 52, DXA is required at Early Termination unless a DXA result is available from within six weeks prior to Early Termination, and follow-up DXA is required at 6 months ( $\pm$  1 month) if the most recent DXA scan was at Week 24 and bone mineral density loss at the lumbar spine (L1-L4) or total hip was  $>$  2% or most recent DXA result was after Week 24 and bone mineral density loss at the lumbar spine (L1-L4) or total hip was  $>$  3%, relative to the parent study baseline. For Early Termination occurring between Week 52 and Week 104, DXA is required at Early Termination unless a DXA result is available from within six weeks prior to Early Termination, and follow-up DXA is required at 6 months ( $\pm$  1 month) if on the most recent DXA, bone mineral density loss at the lumbar spine (L1-L4) or total hip was  $>$  7%, relative to parent study baseline.

- t Endometrial biopsies are to be done per instructions in the parent study. Procedures for handling and shipping biopsy samples to the central laboratory for analysis are described in the Investigator Site File. An endometrial biopsy will have been performed at the parent study Week 24 visit for all patients who participated in MVT-601-3101 only (see MVT-601-3101 protocol for details) and at Week 52 and Early Termination visit for all patients. This procedure is not required at the Early Termination visit in patients whose last dose of study drug was taken during Week 32 or earlier or within four weeks after completion of the Week 52 endometrial biopsy. However, the procedure may be done if it will aid in the evaluation of an ongoing adverse event. An endometrial biopsy at Week 104 is recommended for all patients who complete the open-label extension; however, patients will have the option to opt out.

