- u Please see Appendix 1 for list of protocol-specified analgesics and see the Investigator Site File for information on where and how to obtain protocol-specified analgesic medications by country. At the Week 104 visit, patients who will not be proceeding to another extension study will be re-dispensed or prescribed protocol-specified analgesic drugs, if needed, to ensure sufficient supply until the Follow-Up visit. For patients proceeding to another extension study, refer to the protocol for that next study.
- v Pregnancy test must be negative before the study drug dose is administered. For patients whose Baseline Day 1 visit is conducted on a different day than the parent study Week 24 visit, perform an unscheduled pregnancy test at Baseline Day 1 prior to administering the first dose of study drug.
- w Patients will take the first dose of the study drug for this study once daily starting with the Week 24/Baseline visit (taken at the visit). If necessary, for logistical reasons (eg, delayed availability of study drug supply on site, others), and with sponsor/designee approval, the first dose of open label study drug for MVT-601-3103 may be administered up to 10 days following the parent study Week 24/Baseline visit. If the first dose of study drug is not given during this up to 10-day interval, the parent study follow-up procedures should be followed (ie, adverse event reporting, eDiary completion, etc.). The first dose of study drug for this extension study must not be taken until all parent study Week 24 procedures such as laboratory tests have been completed. Therefore, results of testing required for eligibility (eg, DXA) must be available on or prior to the Week 24/Baseline visit. The last dose of study drug will be taken in the clinic during the Week 104/Early Termination visit.
- x Patients may only take their study-specified analgesics for pain. Analgesics should not be taken prophylactically (ie, in anticipation of pain).
- y The patient will enter her response(s) into an electronic tablet device at the site. On visits when both tablet and paper questionnaires are being performed at the site, the patient should complete the tablet questionnaires before the paper questionnaires.
- z The patient will enter her response onto a paper questionnaire at the site. Paper questionnaires should be done in the following order: PGA for function, EHP Work Domain.

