#### **4.3.1. Inclusion/Exclusion Criteria**

Inclusion Criteria (all inclusion criteria must have been met prior to randomization):

1. Completed 24 weeks of study drug treatment and study participation in either MVT-601-3101 or MVT-601-3102;
2. Has voluntarily signed and dated the informed consent form prior to initiation of any study-specific procedures for MVT-601-3103;

Note: Procedures conducted as part of the parent study that also serve as baseline procedures for this study will be done under the informed consent for the parent study.

3. Is not expected to undergo gynecological surgery or other surgical procedures for treatment of endometriosis (including ablation, shaving, or excision) during the study, including during the Follow-Up Period, and the patient does not desire such treatment during this time frame;
4. Has a negative urine pregnancy test at the Week 24/Baseline visit;
5. Has agreed to continue to use only study-specified analgesic medications during the study and is not known to be intolerant to these;
6. Agrees to continue to use acceptable non-hormonal contraceptive methods as described in Section 4.6 consistently during the Open-Label Treatment Period and for at least 30 days after the last dose of study drug. However, the patient is not required to use the specified non-hormonal contraceptive methods if she:
  - a. Has a sexual partner(s) who was vasectomized at least 6 months prior to the Week 24/Baseline visit;
  - b. Had a bilateral tubal occlusion (including ligation and blockage methods such as Essure™), at least 6 months prior to the Week 24/Baseline visit (patients with Essure must have prior confirmation of tubal occlusion by hysterosalpingogram) and there must be no evidence of post-Essure syndrome;
  - c. Has a non-hormonal intrauterine device (eg, Paragard®) placed in the uterus;
  - d. Is not sexually active with men; periodic sexual relationship(s) with men requires the use of non-hormonal contraception as noted above;
  - e. Practices total abstinence from sexual intercourse, as her preferred lifestyle; periodic abstinence is not acceptable.

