#### **4.5. Removal of Patients from Therapy**

Completion of the Week 104 visit defines completion of the study. Patients may withdraw consent to participate in the study and discontinue treatment at any time for any reason. Investigators or the medical monitor may remove patients from therapy under this protocol for reasons of safety and/or lack of compliance as discussed below. Patients removed from therapy for any reason will undergo the assessments for the Early Termination visit (see the Week 104 visit on the Schedule of Activities, Section 1.1) and will have a Follow-up visit to assess safety approximately 30 days after the end of study drug treatment (ie, after the patient's last dose of study medication). When patients complete the study or early terminate from the study, they must be deactivated from the study in the interactive voice response system/interactive web response system (IVRS/IWRS), eDiary, and tablet device.

The following safety and/or compliance events will result in the removal of patients from therapy either permanently or until the etiology of the problem has been identified and resolved:

- Any adverse event that is intolerable to the patient and that cannot be ameliorated by the use of adequate medical intervention, or that in the opinion of the investigator or medical monitor would lead to undue risk to the patient if dosing continued;
- If it is discovered after enrollment that a patient failed to meet protocol entry criteria and continued participation poses an unacceptable risk to the patient's health;
- If the following liver test abnormalities develop, study drug should be discontinued immediately with appropriate clinical follow-up (including repeat laboratory tests, until a patient's laboratory profile has returned to normal/baseline status):
  - ALT or AST > 8 x ULN; or
  - ALT or AST > 5 x ULN and persists for more than 2 weeks; or
  - ALT or AST > 3 x ULN in conjunction with elevated total bilirubin > 2 x ULN or international normalized ratio (INR) > 1.5; or
  - ALT or AST > 3 x ULN with appearance of fatigue, nausea, vomiting, right upper quadrant pain or tenderness, fever, rash and/or eosinophilia (> 5%);

- 
- QT interval by the Fridericia correction (QTcF) prolongation of more than 500 msec read by a cardiologist;
  - Evidence of endometrial hyperplasia or endometrial carcinoma on endometrial biopsy;

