  - If the patient has a  $\geq 7\%$  loss of bone mineral density at lumbar spine, total hip, or femoral neck compared with the parent study Baseline;
  - If the patient, in the opinion of the investigator or the medical monitor, is grossly noncompliant with the protocol's requirements. Gross noncompliance includes  $< 75\%$  compliance with the study drug over  $> 2$  consecutive months; missing multiple study visits; and persistent ( $> 2$  consecutive months) noncompliance ( $< 50\%$  of the required number of days) with eDiary completion up to Week 52 or persistent ( $\geq 2$  eDiary collection cycles) noncompliance ( $< 50\%$  of the required number of days) with eDiary completion from Week 52 to Week 104. Investigators will follow up with the patient and encourage compliance with study drug or eDiary prior to discontinuing her from the study;
  - If the patient becomes pregnant at any time after providing a signed informed consent form, the patient must be withdrawn immediately (see Section 7.8 for information on pregnancy reporting);
  - Evidence of malignant breast lesion(s) or breast carcinoma on Week 52 or Week 104/Early Termination or most recent mammogram or additional breast imaging (see Section 6.5.2.9 for more information on mammogram at Week 52 or Week 104/Early Termination);

Should a patient fail to attend the clinic for a required study visit within the protocol-defined window, the site should attempt to contact the patient and reschedule the missed visit as soon as possible. The site should also counsel the patient on the importance of maintaining the assigned visit schedule and determine whether the patient can and/or should continue in the study based on previous noncompliance. In cases where the patient does not return for the rescheduled visit or cannot be reached to reschedule the missed visit, the site should make every effort to regain contact with the patient. The site should attempt at least three documented telephone calls and if necessary, a certified letter to the patient's last known mailing address so that they can appropriately be withdrawn from the study with a primary reason of "Lost to Follow-up."

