An endometrial biopsy will have been performed at the parent study Week 24 visit for all patients who participated in MVT-601-3101 (see MVT-601-3101 protocol for details). An endometrial biopsy is required at Week 52 and the Early Termination visit for all patients. This procedure is not required at the Early Termination visit in patients whose last dose of study drug was taken during Week 32 or earlier or within four weeks after completion of the Week 52 endometrial biopsy. However, the procedure may be done if it will aid in the evaluation of an ongoing adverse event. An endometrial biopsy at Week 104 is recommended for all patients who complete the open-label extension ; however, patients will have the option to opt out. Safety monitoring for this study includes physical examination, clinical laboratory tests, pregnancy tests, and adverse event collection at each visit. Clinical chemistries will be collected at each visit. A complete blood count will be collected at Week 24/Baseline, Week 28, Week 36, Week 52, Week 65, Week 78, Week 91, and Week 104. At the Week 24/Baseline visit, Week 52 visit, and Week 104 visit, additional tests include fasting (at least 8 hours, other than water) glucose, lipid profile, and hemoglobin A1c.

Electrocardiograms will be performed at the Week 24/Baseline and the Week 52 visits.

A mammogram will be performed at Week 52 or at Week 104/Early Termination for women who are or become  $\geq 40$  years old during the study (see Section 6.5.2.9).

Bone densitometry will occur at the Week 24/Baseline, Week 36, Week 52, and Week 104/Early Termination visits. Follow-up of bone densitometry findings will proceed according to the rules described in Section 6.5.2.6.

Bone densitometry and ECGs will be submitted for central reading.

Study drug compliance will be reviewed at each visit. Fasting (other than water) for at least 8 hours is required prior to blood sampling on Week 24/Baseline and Week 52/Early Termination visits and for 1 hour after administration of the study drug in the clinic. Laboratory requisitions must indicate whether or not the patient was not fasted for their chemistry and lipid testing.

Refer to the Schedule of Activities (see Section 1.1) for information about study procedures during the Open-Label Treatment Period.

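### The mandatory Early Termination biopsy rule lists two timing exceptions but not pregnancy, so as written it reaches patients withdrawn because they are pregnant

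*Protocol*

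**What the plan says.** The file holds two versions of the protocol. This point concerns the later one, which contains Section 4.7 on COVID-19.

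The Early Termination biopsy rule appears in three places:

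- Section 6.3: "An endometrial biopsy is required for all patients at the Early Termination visit except for patients whose last dose of study drug" fell by the end of Week 32, or within four weeks of the Week 52 biopsy.
- Section 6.2: "An endometrial biopsy is required at Week 52 and the Early Termination visit for all patients". The same two exceptions follow.
- Table 1-1, footnote t: biopsy for everyone at Week 52 and at Early Termination, then "This procedure is not required at the Early Termination visit in patients whose last dose of study drug was taken during Week 32 or earlier", with the same second window.

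The Week 104 biopsy is handled differently. It is "recommended for all patients who complete the open-label extension; however, patients will have the option to opt out".

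Two statements in Section 4.5 decide who reaches the Early Termination visit:

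- "Patients removed from therapy for any reason will undergo the assessments for the Early Termination visit".
- "If the patient becomes pregnant at any time after providing a signed informed consent form, the patient must be withdrawn immediately".

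Pregnancy is not mentioned in any of the three statements of the biopsy rule.

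**The concern.** Pregnancy is a withdrawal reason that the protocol itself lists. The withdrawal pathway leads to a visit at which an intrauterine procedure is mandatory, and the list of exceptions is closed and concerns timing only. Followed literally, the text tells a site to sample the uterus of a patient whose pregnancy is the reason she is leaving. A site that rightly declines has then omitted a procedure that the text calls required.

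What is at stake is the safety of a written instruction, not the inference from the trial. The biopsy does not enter the responder endpoints or the bone mineral density comparison.

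**Working it through.** The protocol gives no figure to reproduce here. The check is to follow a pregnant patient through the rules of the later version.

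1. **Withdrawal.** Section 4.5 withdraws her at once. Section 4.6 also says that patients who become pregnant are withdrawn, and adds follow-up of the pregnancy to its outcome.
2. **Visit.** Section 4.5 sends patients removed for any reason to the Early Termination assessments. Section 6.3 separately requires an Early Termination visit of everyone who withdraws before Week 104. Both routes include her.
3. **Biopsy.** Sections 6.2 and 6.3 and footnote t make the biopsy mandatory at that visit.
4. **Exceptions.** There are two, both defined by the date of the last dose. Neither depends on the reason for leaving.
5. **Opt-out.** Section 6.3 describes Early Termination procedures as the same as those of Week 104, where the biopsy is voluntary. That does not help her, because the next sentence of Section 6.3 makes the Early Termination biopsy required. The opt-out in Section 6.2 and footnote t is confined to patients who complete the extension.

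**Reach of the two exceptions.** Assume that the Week 52 biopsy is done at Week 52.

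- First window, from Week 24 to Week 32: 32 − 24 = 8 weeks, or 9 if the whole of Week 32 is counted.
- Second window, from Week 52 to Week 56: 4 weeks.
- Total exempt: 8 + 4 = 12 weeks, or 9 + 4 = 13 weeks.
- Remaining part of the 80-week treatment period: 80 − 13 = 67 weeks, or 80 − 12 = 68 weeks.

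For most of the treatment period, then, a last dose falls outside both exceptions. This shows how far the rule extends. It is not an estimate of how often a pregnancy would meet it.

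**The case against.** **Unseen text.** The text of the later version available here stops within Section 6.5.2.6. The biopsy section (6.5.2.7) and the pregnancy section (7.8) come after it, and these are natural places for an exemption. Both pregnancy statements, in Sections 4.5 and 4.6, point to Section 7.8. Footnote t refers the conduct of biopsies to the parent-study instructions, which are also not shown. This objection stands in part. A reader might infer that the protocol as a whole lacks the safeguard, and the documents do not support that. An exemption elsewhere would, however, conflict with three explicit statements that cover all patients, and the same edit would remove the conflict. Section 7.8 of the earlier version brings a pregnant patient back for an Early Termination visit, but that section is superseded and does not show what the later one says.

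**Clinical judgement.** Following a pregnancy to its outcome is hard to reconcile with an intention to biopsy, and an investigator would be unlikely to sample a woman known to be pregnant. This stands, and it is the main reason why the point is minor.

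**A stronger reading that is not supported.** A reader might go on to infer that the protocol leaves out a negative pregnancy test before the biopsy. The visible text asks for a negative result at entry ("Has a negative urine pregnancy test at the Week 24/Baseline visit") and before dosing ("Pregnancy test must be negative before the study drug dose is administered"), and does not name the biopsy. But Table 1-1 schedules a urine test at both Week 52 and Week 104/Early Termination, and Section 6.2 lists pregnancy tests among the safety checks at each visit. The clinical laboratory section has the sites run the tests themselves. The text is silent on the order of the test and the biopsy within a visit; it does not state a wrong order. Any preconditions may sit in the parent-study instructions.

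For the same reason, the wider spacing of scheduled visits after Week 52 does not measure the risk. A test is due at the biopsy visit itself, so the age of the previous result matters only if the current test is skipped or ignored.

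**Conclusion.** The point holds in a narrow form. Sections 6.2 and 6.3 and footnote t, combined with Section 4.5, require a biopsy in a patient withdrawn for pregnancy unless her last dose falls in one of the two timing windows.

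It is a minor correction of safety wording. No endpoint, estimate or analysis changes, and no number of affected patients is claimed because the documents give no pregnancy rate. The conclusion rests on the visible text of the later version. If Section 6.5.2.7, Section 7.8 or the parent-study instructions already exempt pregnancy, what remains is an inconsistency between sections.

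**What to change.** Add a third exception in Sections 6.2 and 6.3 and in footnote t of Table 1-1, for example: no protocol endometrial biopsy is performed in a patient who is pregnant or who has a positive urine pregnancy test at that visit. Then check Sections 6.5.2.7 and 7.8 and make them agree; if they already say this, only the three statements above need the edit.

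The cost is one sentence in each of three places at the next amendment. The urine test is already scheduled at the relevant visits, so no procedure is added, and at most a few biopsies are not collected.

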Determination of bone mineral density by DXA at Early Termination and follow-up of findings will proceed according to the following rules:

- For Early Termination occurring between Week 24 and Week 52:
  - For Early Termination occurring before Week 36, DXA is not required at Early Termination visit unless it will aid in the assessment of an adverse event.
  - Follow-up DXA required at 6 months ( $\pm 1$  month) if most recent DXA bone mineral density loss at lumbar spine (L1-L4) or total hip was  $> 2\%$  relative to the parent study baseline.
  - For Early Termination occurring after Week 36, DXA is required at Early Termination unless a

DXA result is available from within six weeks prior to Early Termination.

- Follow-up DXA is required at 6 months ( $\pm$  1 month) if the most recent DXA scan was at Week 24 and bone mineral density loss at the lumbar spine (L1-L4) or total hip was  $> 2\%$ , relative to the parent study baseline.
- Follow-up DXA is required at 6 months ( $\pm$  1 month) if on the most recent DXA, bone mineral density loss at the lumbar spine (L1-L4) or total hip was  $> 3\%$ , relative to the parent study baseline.
- For Early Termination occurring between Week 52 and Week 104:
  - DXA is required at Early Termination unless a DXA result is available from within six weeks prior to Early Termination.
  - Follow-up DXA is required at 6 months ( $\pm$  1 month) if on the most recent DXA, bone mineral density loss at the lumbar spine (L1-L4) or total hip was  $> 7\%$ , relative to parent study baseline.
- If patients have 6-month post-treatment follow-up scans that show bone loss of  $> 1.5\%$  at the lumbar spine and/or  $> 2.5\%$  at total hip compared with parent study baseline, patients are strongly encouraged to come back to the clinic for an additional post-treatment follow-up scan 12 months from the date of the last dose of the study drug.
- If patients have 12-month post-treatment follow-up scans that show bone loss of  $\geq 3\%$  at the lumbar spine and/or total hip compared with parent study baseline, patients are referred to and strongly encouraged to see a bone specialist for further evaluation of the bone loss.

Note: When a patient is referred to a bone specialist for evaluation and management, Myovant will provide a Bone Consultation Letter to the investigator for this additional bone consult and will request the site to provide a summary of the evaluation and management plan once the consultation is complete.

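### Section 6.3 leaves the Early Termination bone scan to the investigator's judgement where the synopsis and Schedule footnote s require it, so a woman who leaves in the second year may have no bone value after Week 52

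*Protocol*

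**What the plan says.** Section 6.3, the section a site consults for an Early Termination visit, says of DXA: "Bone densitometry may be performed at the investigator's discretion, if it aids in follow-up of an ongoing adverse event(s". It sets no limit by time of termination. Earlier in the same paragraph it says "The Early Termination visit procedures are identical to those of Week 104", and the Week 104/Early Termination column of the Schedule of Activities includes bone densitometry.

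Elsewhere the protocol gives a rule that depends on timing:

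- **Synopsis, Study Design.** Before Week 36 the exit scan is not required unless it helps to assess an adverse event. After Week 36, and again for exits between Weeks 52 and 104, "DXA is required at Early Termination unless a DXA result is available from within six weeks prior to Early Termination".
- **Schedule of Activities, footnote s.** The same rule: "For Early Termination occurring after Week 36 and before Week 52, DXA is required at Early Termination unless a DXA result is available" from the preceding six weeks, and "For Early Termination occurring between Week 52 and Week 104, DXA is required at Early Termination unless a DXA result is available" on the same terms.
- **Section 6.2.** "Bone densitometry will occur at the Week 24/Baseline, Week 36, Week 52, and Week 104/Early Termination visits". Section 4.1 says the same for each patient.

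Two further rules interact with this one. For exits between Weeks 52 and 104, the synopsis requires a six-month follow-up scan "if on the most recent DXA, bone mineral density loss at the lumbar spine (L1-L4) or total hip was" more than 7%. Section 4.5 calls for removal from therapy at a 7% or greater "loss of bone mineral density at lumbar spine, total hip, or femoral neck compared with the parent study Baseline".

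**The concern.** Two sites could treat the same leaver differently and each could claim compliance. One, following the synopsis or the Schedule, would scan. The other, following the DXA sentence in Section 6.3, would scan only if an adverse event gave a reason.

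Percent change in bone mineral density is a named safety endpoint at Week 52 and Week 104, and a mean with a 95% confidence interval is planned at Week 104. For a woman who leaves in the second year, the exit scan is the only scheduled bone measurement after Week 52. If it is skipped, her second-year bone change is unobserved and the post-treatment follow-up rule has no new value to act on. If it is done only when an adverse event prompts it, the exit values that exist come from a selected group.

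**Working it through.** The protocol states no figure to reproduce. The check sets the rules side by side by time of exit, then traces the follow-up trigger.

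**1. Where the rules diverge.** Inputs: scans at Weeks 24, 36, 52 and 104/Early Termination (Section 6.2); six-week exemption (synopsis, footnote s). Assumption: the Week 36 and Week 52 scans are done on schedule, so the exemption lasts until about Week 36 + 6 = 42 and Week 52 + 6 = 58.

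| Time of exit | Synopsis and footnote s | DXA sentence in Section 6.3, read alone | Conflict in practice |
|---|---|---|---|
| Before Week 36 | Not required; may help assess an adverse event | Adverse-event driven | No |
| Week 36 to about 42 | Exempt, recent scan | Adverse-event driven | No |
| About Week 42 to 52 | Required | Adverse-event driven | Yes, 52 − 42 = 10 weeks |
| Week 52 to about 58 | Exempt, recent scan | Adverse-event driven | No |
| About Week 58 to 104 | Required | Adverse-event driven | Yes, 104 − 58 = 46 weeks |

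**2. Age of the last scan if the exit scan is skipped.** For exit at Week w in the second year, the last scheduled scan is w − 52 weeks old: 58 − 52 = 6 weeks at the start of the conflict window, rising to 104 − 52 = 52 weeks (52 × 7 = 364 days) at its end.

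**3. Follow-up trigger, exits between Weeks 52 and 104.** Let L be the percent loss at lumbar spine or total hip on the Week 52 scan.

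- Follow-up is triggered if L > 7 on the most recent DXA.
- Removal is called for if L ≥ 7 at either of those sites, or if femoral neck loss is 7% or more.
- Every value that meets the trigger also meets the removal rule. A woman who continued treatment under the rules therefore had L < 7.
- Without an exit scan or an unscheduled scan, Week 52 remains her most recent DXA, and L < 7 cannot meet L > 7.

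The synopsis makes the 12-month scan, and then the bone-specialist referral, depend on what the preceding follow-up scan shows. Those steps have nothing to start from if the six-month scan is never triggered.

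**4. Follow-up trigger, exits between Weeks 36 and 52.** The triggers are more than 2% if the latest scan was at Week 24 and more than 3% otherwise. Both can still be met on an existing scan, so the consequence in step 3 is confined to the second year.

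**The case against.** The strongest reply is that Section 6.3 waives nothing. Its sentence grants permission and never says the scan is not required. It follows a biopsy sentence of similar form that plainly concerns exempt patients, and the general rule in the same paragraph imports the Week 104 procedures. The synopsis, Sections 4.1 and 6.2, the Schedule and footnote s all point the other way. Many sites would scan regardless.

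This shows that the permissive reading is not the only one, but it does not remove the conflict. A specific sentence on DXA that follows a general one is naturally read as qualifying it. The contrast with the biopsy, which is stated as required with listed exceptions, supports that reading. The pointers in Section 6.3 to Section 6.5.2.6 are worded for follow-up of findings, so they do not settle whether the exit scan is done.

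Three stronger readings are tempting and are not supported:

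- **That the follow-up trigger can never operate once an exit scan is skipped.** It can operate for exits between Weeks 36 and 52, for a woman removed because of her Week 52 scan, and after an unscheduled DXA, although Section 6.4 asks for sponsor approval of that unless it is urgent. Section 4.5 also allows removal to be temporary, so a woman could resume after a large loss.
- **That the main bone analysis is compromised.** The comparison with −2.2% in Group A is made at Week 52, before any second-year exit. The Week 104 interval is described as supportive, and whether exit scans enter it depends on visit mapping not set out in the protocol text available.
- **That a number of affected women can be given.** The protocol states neither a second-year exit rate nor a rate of omitted scans.

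**Conclusion.** The inconsistency is real and stands in the current text. Section 6.3 attaches no time limit to a discretionary scan that the synopsis and footnote s require after Week 36, and it disagrees with Section 6.2 and with its own general rule.

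On the permissive reading, the rules differ for exits over about 10 weeks of the first year and 46 of the 52 weeks of the second. A second-year leaver's last scheduled bone value could be up to about 52 weeks old. For a woman who continued after Week 52 without an unscheduled scan, the trigger of more than 7% could generally not be met. The Week 104 bone summaries would be selective only to the extent that exit scans enter them and that sites scan on adverse events alone.

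These conclusions assume on-time scans at Weeks 36 and 52 and application of the removal rule as written. In the text available, the current Section 6.5.2.6 breaks off before its Early Termination rules. Its Amendment 2 wording matches the synopsis, but agreement of the current wording could not be confirmed.

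**What to change.** Reconcile Section 6.3 with Section 6.2, the synopsis, Schedule footnote s and Section 6.5.2.6, so that a single Early Termination DXA rule appears everywhere, including when adverse-event discretion applies. The simplest form is to state the rule once and have the other places refer to it for whether the scan is done as well as for follow-up of findings. Which rule applies is the sponsor's clinical decision. When settling it, the sponsor should check how the rule works with the follow-up trigger of more than 7% and the removal rule at 7% or more.

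The cost is about one sentence in Section 6.3 and a consistency check of the other places, in the next amendment or a clarification letter to sites.
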